2.4. Secondary Endpoints

The secondary endpoints are as follows:

- Change from baseline in neurotransmitter CSF metabolite HVA (at 48 weeks after administration)
- Change from baseline in PET imaging of putaminal-specific L-6-[¹⁸F] fluoro-3,4-dihydroxyphenylalanine (¹⁸F-DOPA) PET uptake at the end of the Trial Phase (8 weeks after administration) and the Extension Phase (48 weeks after administration)
- Change from baseline in neurotransmitter CSF metabolites 5-HIAA and 3-OMD at 8 and 48 weeks after administration
- Attainment of motor milestones
- Motor development as assessed by the PDMS-2
- Cognitive and language development as assessed by Bayley-III
- Change in EQ-5D-Y
- Change in body weight
- Assessment of AADC-specific symptoms
- Overall safety profile characterized by type, frequency, severity, timing, and relationship to study treatment of any TEAEs, neurological examination findings, brain imaging, or laboratory abnormalities.

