7.5.5. Describing Adverse Event Relationship to Gene Therapy or Surgery

The investigator should provide an assessment of the relationship of the AE to the gene therapy, the cannula, or the neurosurgery (ie, whether there is a reasonable possibility that the gene therapy, the cannula, or the neurosurgery caused the AE) using the considerations outlined in [Table 4](#).

Table 4: Relationship of Gene Therapy to Adverse Event

Relationship	Description
Probable	A clinical event in which a relationship to the gene therapy seems probable because of such factors as consistency with known effects of the drug; a clear temporal association with the use of the drug; lack of alternative explanations for the event.
Possible	A clinical event occurring coincident with administration of the gene therapy and which may or may not be explained by concurrent disease or other drugs or chemicals.
Unlikely	A clinical event with a temporal relationship to the gene therapy exposure that does not preclude causality but for which there is a clear alternate cause that is more likely to have caused the AE than gene therapy. Such alternatives include a concomitantly administered drug, the subject's disease state, other medical conditions, or environmental factors.
Unrelated	A clinical event, for which a relationship to the gene therapy seems improbable because of factors such as inconsistency with known effects of the gene therapy, lack of a temporal association with gene therapy administration, and/or presence of alternative explanations for the event. Alternative explanations might include a known relationship of the AE to a concomitant drug, medical history of a similar event, the subject's disease state, other medical conditions, or environmental factors.

Abbreviations: AE, adverse event

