3.2. Safety Population

The safety population will consist of all subjects enrolled in the study who have received any amount of study drug.

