7.1.1. Treatment-emergent Adverse Events

A TEAE is any AE that occurs post study drug administration. If onset date is missing, the AE is considered as TEAE.

An overall summary of TEAEs will be provided for number and percentage of subjects experiencing the following:

- TEAE.
- TEAE related to gene therapy.
- TEAE related to surgical device.
- TEAE related to neurosurgical procedure.
- TEAE related to F-DOPA.
- TEAE by severity.
- TEAE leading to withdrawal.
- TEAE of special interest (TEAESI: dyskinesia and cerebrospinal fluid leakage)
- Treatment emergent SAE (TESAE)
- TESAE and reasons for SAE
- TESAE related to gene therapy.

In the overall summary of TEAEs table, besides tabulating the number and percentage of subjects, the total number of TEAE episodes will also be provided. If a subject has repeated episodes of a particular TEAE, all episodes will be counted in the summary table.

Summary of number and percentage of subjects experiencing a TEAE will be presented for the following:

- TEAE by PT in descending order of incidence
- TEAE by SOC and PT
- TEAE related to gene therapy by SOC and PT.
- TEAE related to surgical device by SOC and PT.
- TEAE related to neurosurgical procedure by SOC and PT.
- TEAE related to F-DOPA by SOC and PT.
- TEAE by SOC, PT, and severity.

- TEAE leading to withdrawal by SOC and PT.
- TEAESI by SOC and PT.
- TESAE by SOC and PT
- TESAE related to gene therapy by SOC and PT

In the summary tables listed above, the percentage of subjects with TEAEs will be calculated by dividing the number of subjects who have experienced the event by the total number of subjects in the safety set. If a subject has repeated episodes of a particular TEAE, only the most severe episode, or the episode with the strongest causal relationship to study drug, will be counted in the summary tables.

A subject with more than one type of TEAE in a particular SOC will be counted only once in the total of subjects experiencing TEAEs in that particular SOC. Since a subject could have more than one type of TEAE within a particular SOC, the sum of subjects experiencing different TEAEs within the SOC could appear larger than the total number of subjects experiencing TEAEs in that SOC. Similarly, a subject who has experienced a TEAE in more than one SOC will be counted only once in the total number of subjects experiencing AEs in all SOCs.

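### The SAP's F-DOPA-related event tables start their clock at gene therapy, so a dated reaction to the Baseline PET injection that starts before dosing generally cannot enter them

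*SAP*

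**What the plan says.** SAP 7.1.1 sets the onset rule for its adverse event summaries: "A TEAE is any AE that occurs post study drug administration". It adds one default: "If onset date is missing, the AE is considered as TEAE". The study drug is eladocagene exuparvovec, given on Dosing Day (Protocol Table 1). Protocol 8.3.2.2 uses the same anchor but also counts events that worsen after dosing. The SAP's definition has no worsening clause, although SAP 4.4 declares no change from the protocol.

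Two outputs in SAP 7.1.1 concern the PET tracer. One is a row in the overall summary, "TEAE related to F-DOPA". The other is a separate table, "TEAE related to F-DOPA by SOC and PT". Percentages in the organ-class and preferred-term tables are formed "by dividing the number of subjects who have experienced the event by the total number of subjects in the safety set", and that set is "all subjects enrolled in the study who have received any amount of study drug" (SAP 3.2).

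The tracer has its own schedule. Protocol 2.4 makes "Change from baseline in PET imaging of putaminal-specific" F-DOPA uptake a secondary endpoint at Weeks 8 and 48, which requires a pre-treatment scan. Protocol Table 1 places that scan at Visit 2 (Baseline, Week -1) and the next at Week 8. Table 2 adds Week 48. Protocol 7.3.1 describes intravenous administration of F-DOPA for the scan.

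On causality, Protocol 7.5.5 asks "whether there is a reasonable possibility that the gene therapy, the cannula, or the neurosurgery caused the AE". Protocol 7.5.4 lists relationship to gene therapy and to surgery. Neither section names F-DOPA.

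**The concern.** A table of events related to a product should cover the time during which that product was given. Here the sponsor chose to tabulate events related to F-DOPA, but the onset rule belongs to a different product and starts after the first F-DOPA exposure.

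The data are not the obstacle. Adverse events are recorded from consent (Protocol 7.5.8), Table 1 marks their collection at the Baseline visit, and SAP 7.1 codes all events from consent. Only the restriction to treatment-emergent events removes them from the tables. In a study planned for a minimum of three children, a single event decides whether the F-DOPA row reads zero or not. Someone reading only the tables could conclude that no F-DOPA reaction occurred when one had been recorded at Baseline.

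**Working it through.** The plan states no figure on this point, so there is none to reproduce. The check is a count of exposures, followed by an illustration under stated assumptions.

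**Exposures per child, from Protocol Tables 1 and 2**

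| F-DOPA injection | Relative to dosing | Can a dated reaction that starts before the next study step enter the F-DOPA tables? |
|---|---|---|
| Baseline, Week -1 | Before | No, if it starts before dosing (exceptions below) |
| Week 8 | After | Yes |
| Week 48 | After | Yes |

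Injections that cannot normally contribute: 1/3 = 33% per child. For the minimum of three children, all followed through Week 48: 3 × 3 = 9 scheduled injections, 3 × 2 = 6 after dosing, so 3 of 9 fall outside.

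**Exceptions.** A Baseline reaction with no recorded onset date counts as treatment-emergent under the SAP. Under the protocol's definition, so does one that worsens after dosing.

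**Direction.** Among dosed children the denominator is the safety set under either rule. Starting the count earlier can add F-DOPA-related events but remove none. The planned count is therefore at or below the full count, never above it.

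**When a subject percentage changes.** It changes only if a child reacts at Baseline and has no later F-DOPA-related treatment-emergent event. With three children and one such case, the table shows 0/3 = 0% where the full count is 1/3 = 33%.

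**Illustration of expected size.** The documents give no reaction rate. Assume a risk p per injection, the same at each injection and independent between them. The expected share of subjects with at least one reaction is:

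- planned tables, two injections: 1 − (1 − p)²
- all three injections: 1 − (1 − p)³

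For p = 5%: 1 − 0.95² = 9.75%, and 1 − 0.95³ = 14.26%. The difference, 4.51 points, equals p(1 − p)² = 0.05 × 0.9025, which is the chance of a Baseline reaction with none later.

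| Assumed p | Planned tables | All injections | Ratio |
|---|---|---|---|
| 1% | 1.99% | 2.97% | 0.67 |
| 2% | 3.96% | 5.88% | 0.67 |
| 5% | 9.75% | 14.26% | 0.68 |
| 10% | 19.0% | 27.1% | 0.70 |
| 20% | 36.0% | 48.8% | 0.74 |

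Under these assumptions the tabulated percentage would be, in expectation, about 67% to 74% of the all-injection value. These figures illustrate the mechanism and do not estimate a bias in this trial.

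**The case against.** The strongest reply is that nothing is lost from the report. SAP 7.1.1 lists all occurrences of all adverse events for each child, and with so few children a listing is easy to read. The outputs are also openly labelled as treatment-emergent. F-DOPA safety is neither an objective nor an endpoint; the tracer serves a pharmacodynamic measurement. A post-dose F-DOPA row has a sensible use of its own, which is to separate tracer-attributed events from those attributed to gene therapy, device or procedure. All of this stands, and it limits the importance of the point. It does not explain why a table the sponsor chose to produce should leave out the first of three planned exposures.

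A reader might infer more than the documents support:

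- **That every Baseline reaction is excluded.** The missing-onset rule and the protocol's worsening clause are exceptions.
- **That the tracer's event rate is shown to be understated.** No reaction rate is given, the SAP does not set out to estimate a rate per injection, and a subject percentage changes only in the circumstance described above. It is also tempting to say that half the exposures (1 of 2) are lost by Week 8, but SAP 7.1.1 specifies no Week 8 cut for these tables.
- **That Week 8 tracer reactions contaminate the primary safety summaries.** This presumes that sites have no way to attribute an event to F-DOPA. The eCRF is not among the documents, and the SAP's tabulation of that relationship suggests that it is collected. Protocol Table 4 also lets investigators cite another administered drug as the alternative cause.

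A child given F-DOPA at Baseline but never dosed would fall outside the safety set. That is a hypothetical case, and such a child leaves both numerator and denominator.

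**Conclusion.** The point holds as a mismatch between the F-DOPA tables and the F-DOPA exposure. It rests on three readings of the text: treatment-emergent status starts at gene therapy, both F-DOPA outputs are restricted to treatment-emergent events, and the Baseline PET comes before dosing. The exposure count further assumes that each child has all three scheduled scans.

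The effect on the results can run only towards too few events, and its size cannot be fixed from the documents. This is a reporting matter. It does not touch the primary HVA analysis, and nothing in the documents shows an effect on the cannula safety summaries. It is worth correcting because the correction costs almost nothing. The missing mention of F-DOPA in the protocol's causality sections is a secondary alignment point.

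**What to change.** In SAP 7.1.1, define the F-DOPA-related outputs as adverse events related to F-DOPA with onset from the first F-DOPA injection, in all children given F-DOPA. Show them by injection (Baseline, Week 8, Week 48) or as pre-dose and post-dose. The post-dose part keeps the information in the present treatment-emergent row. A smaller alternative is to keep the present outputs and add one row for F-DOPA-related events before dosing. Either way the cost is SAP wording and one changed table shell, since the events themselves are already recorded.

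Separately, confirm that the eCRF has a field for relationship to F-DOPA. If it does, add F-DOPA to Protocol 7.5.4 and 7.5.5 at the next amendment, so that the protocol asks for what the SAP tabulates. If it does not, the cost is higher: a database change and possibly retrospective attribution of events already recorded.

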7.5.4. Adverse Event Recording

All AEs (both serious and nonserious) that occur in subjects during the AE reporting period (screening until the Final Study Visit) must be recorded, whether or not the event is considered drug related.

All AEs are to be recorded in the source documents and on the eCRF using concise medical terminology; whenever possible, terms contained in the Medical Dictionary for Regulatory Activities (MedDRA) should be employed. In addition, the following information should be recorded:

- Indication of whether the event is serious or nonserious (see Section 7.5.2)
- Relationship to gene therapy (see Section 7.5.5)

- Relationship to surgery
- Severity of the event (see Section 7.5.6)
- Onset date
- Resolution date, or date of death
- Action taken
- Outcome of the event

Classification of the event as serious or nonserious determines the reporting procedures to be followed.

The investigator is to report all directly observed AEs and all AEs spontaneously reported by the study subject/parent(s)/legal guardian/legally acceptable representative. In addition, each study subject/parent(s)/legal guardian/legally acceptable representative will be questioned about AEs at each scheduled clinic visit after gene therapy administration or during any telephone contact with the subject/parent(s)/legal guardian/legally acceptable representative. The type of question asked should be open-ended, for example, “How have you been feeling?” or a similar type of query.

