7.5.8. Adverse Event Reporting Period

Investigator site reporting requirements for AEs are summarized in [Table 6](#).

Table 6: Investigator Site Requirements for Reporting Adverse Events

Event	Recorded on the eCRF	Reported to PTC Pharmacovigilance Within 24 Hours of Awareness
Serious AE	All	All
Nonserious AE	All	None
AESIs	All	All
Other, eg, exposure to the gene therapy during pregnancy or breastfeeding, and occupational exposure	All (regardless of whether associated with an AE), except occupational exposure	All (regardless of whether associated with an AE)

Abbreviations: AE, adverse event; AESI, adverse event of special interest; eCRF, electronic case report form

The first day of AE reporting will coincide with the date of signing of informed consent and including a minimum of 30 calendar days after the Final Study Visit (Month 60), except as

described in Section 7.5.4. In addition, SAEs occurring in a subject after the study period should be reported to the sponsor if the investigator becomes aware of them.

The medical monitor will review all AEs and SAEs as they are reported from the site. The DSMB will conduct a review of safety data as outlined in the DSMB charter. The DSMB will monitor ongoing safety data to ensure subject well-being, safety, and study integrity.

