8.3.2.2. Primary Safety Analysis

The primary safety analysis will focus on TEAEs that are defined as AEs with a start date after or worsen after receiving eladocagene exuparvovec.

The time of gene therapy administration will be the start time of the first infusion. All AEs reported will be coded using MedDRA. The number and proportion of subjects reporting TEAE will be summarized by System Organ Class (SOC) and by Preferred Term (PT) within SOC. Summaries will also be provided for each severity grade, relationship to cannula device, to gene therapy, and to neurosurgical procedure, and AEs of special interest.

Serious Adverse Events will be summarized using SOC and PT.

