7. SAFETY ANALYSES

7.1. Adverse Events

All AEs (serious and non-serious) occurring after completion of the informed consent process up to required reporting period, regardless of relationship to study drug, will be included and classified by SOC and PT using the MedDRA version 26.0.

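### The SAP's rule for missing AE onset dates has no exception for a resolution date before dosing, so an undated event that provably ended before surgery could be tabulated as treatment-emergent.

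*SAP*

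**What the plan says.** - **Definition in the SAP (7.1.1):** "A TEAE is any AE that occurs post study drug administration".
- **Missing-date rule, the next sentence of SAP 7.1.1:** "If onset date is missing, the AE is considered as TEAE". No condition is attached. Neither the SAP's missing-data section (4.3.1) nor any other part of either document adds one.
- **Definition in the protocol (8.3.2.2, primary safety analysis):** TEAEs are "AEs with a start date after or worsen after receiving eladocagene exuparvovec". The reference time is also fixed there: "The time of gene therapy administration will be the start time of the first infusion". The protocol has no missing-date rule.
- **Collection period:** protocol 7.5.8 says "The first day of AE reporting will coincide with the date of signing of informed consent", and SAP 7.1 takes in "All AEs (serious and non-serious) occurring after completion of the informed consent process". Protocol Table 1 places Screening at Weeks -10 to -2 and marks AE collection at the Baseline visit, before dosing.
- **Data items:** protocol 7.5.4 requires an onset date for each AE and also "Resolution date, or date of death".
- **Tabulation:** SAP 7.1.1 divides by all subjects in the safety set and counts each subject once per term. Its overall summary also counts episodes. All AE occurrences are listed by subject.

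**The concern.** A default is meant for events whose timing is unknown. This one also covers events whose timing is known in the only respect that matters: a child may have no recorded onset date but a resolution date before Day 1. Such an event cannot have started or worsened after the infusion, yet the SAP puts it in the tables meant to describe what followed it.

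The primary safety question is which events are associated with giving the vector through this cannula. With a planned minimum of 3 children, a single wrongly counted event would be visible in a preferred-term percentage. SAP 4.4 also declares no change from the protocol's analysis, whereas the literal rule departs from the protocol's TEAE definition for this class of event.

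**Working it through.** The plan gives no figure to reproduce on this point. The check is a comparison of rules, followed by the arithmetic of one misclassified subject.

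**Step 1. Apply each rule to each pattern of dates.**

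| Onset date | Resolution date | SAP missing-date rule | SAP and protocol definitions | With a pre-dose resolution exception |
|---|---|---|---|---|
| Missing | Before the dosing date | TEAE | Not a TEAE | Not a TEAE |
| Missing | On or after the dosing date, or ongoing | TEAE | Cannot be decided | TEAE |
| Missing | Missing | TEAE | Cannot be decided | TEAE |

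Only the first row is an error. In the other two the timing is unknown and counting the event is a reasonable conservative choice.

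**Step 2. Can the first row occur?** It needs an AE recorded before dosing, no onset date, and a resolution date before Day 1. The collection rules allow all three. Recording starts at consent, which at the Screening visit is 2 to 10 weeks before dosing, and resolution dates are collected.

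**Step 3. How often?** The documents give no missing-date rate. With k pre-dose AEs and a probability m that an onset date is missing, both assumed, the chance of at least one undated pre-dose AE is 1 − (1 − m)^k:

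- k = 5, m = 1%: 1 − 0.99^5 = 4.9%
- k = 10, m = 2%: 1 − 0.98^10 = 18.3%
- k = 20, m = 10%: 1 − 0.90^20 = 87.8%

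The range is too wide to settle the frequency. Each value also overstates the problem, because the event must in addition have a recorded pre-dose resolution date.

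**Step 4. Effect of one misclassified subject.** The denominator is the safety set of n subjects, so the shift in a preferred-term incidence is 100/n points:

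- n = 3 (the documented minimum): 33.3 points
- n = 5 (assumed): 20.0 points
- n = 10 (assumed): 10.0 points

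These are maxima. If the child also has a genuine treatment-emergent event under the same term, the child is already counted and the percentage does not move. The episode total in the overall summary rises by one in either case.

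**The case against.** The strongest defence is that this is a sensible default. It errs towards reporting harm, in a descriptive study with no formal hypothesis testing. Read with the sentence before it, it can be taken as a rule for unknown timing only. Onset date is a required item, monitors check eCRF completeness (protocol 9.1.6), and every AE is listed, so a reader can see a pre-dose resolution date. Most of this stands and is why the point is minor. But a programmer will apply the sentence as written, and a listing lets a reader trace the error without correcting the table.

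Four stronger readings are tempting, and the documents do not support them.

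- **That partial onset dates are also counted as missing.** The SAP does not say so. It is silent on partial dates, which is a gap and not a stated wrong rule.
- **That pre-dose events do enter the primary safety tables.** This is possible under the rule, but nothing shows that it happens.
- **That such events would be credited to surgery, cannula or gene therapy.** Protocol 7.5.5 has the investigator judge each relationship, and lack of temporal association is among its grounds for calling an event unrelated. SAP 7.1.1 tabulates related events separately. An event over before surgery should therefore reach mainly the all-causality counts. One narrow exception is the table of events related to F-DOPA: the first scan is at Baseline, so an undated reaction to it that ended before dosing could appear there.
- **That a large share of undated events is affected.** With consent 2 to 10 weeks before dosing, the pre-dose share of time to Week 8 is 2/(2+8) = 20% to 10/(10+8) = 56%. This does not measure the defect. It concerns events that began before dosing, not those that ended before it. It also assumes events spread evenly in time, which is implausible around neurosurgery. The SAP's TEAE tables state no Week 8 cut; to Week 260 the same calculation gives 2/262 = 0.8% to 10/270 = 3.7%.

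A broader exception, removing undated events that began before dosing and did not worsen, would also go too far. Protocol 7.5.6 records only the highest grade per episode and protocol 7.5.4 lists no worsening date, so absence of worsening may not be derivable. Events that worsened after surgery, which the protocol counts as TEAEs, could be dropped.

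**Conclusion.** The point holds in a narrow form. As written, SAP 7.1.1 would tabulate as treatment-emergent an undated AE that its own resolution date places wholly before surgery, against the definitions in both documents. This is a stated rule that gives a wrong result for one identifiable class of event.

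The effect is at most 33 percentage points on one preferred term at n = 3, and less with more subjects. It requires that such an event occurs and that the child has no other event under that term. That such events are probably rare is a judgement based on onset date being a required and monitored item; the documents give no rate. The severity is minor. The reason to act is that the correction is specific and nearly free.

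**What to change.** Replace the missing-date sentence in SAP 7.1.1 with:

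> *If the onset date is missing, the AE is considered a TEAE unless its resolution date is before the date of the first infusion.*

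Undated AEs that are ongoing at dosing, that resolve on or after the dosing date, or that have no resolution date remain TEAEs, so the conservative default is kept wherever timing is uncertain. No judgement about worsening is needed, because an episode that has ended cannot worsen.

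The cost is one SAP sentence and one programming condition on a date already collected. The only downside is a possibly slightly lower TEAE count; the removed events still appear in the AE listing.

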2.3. Primary Endpoints

The primary efficacy endpoint is the change from baseline in HVA metabolite levels at the end of the Trial Phase (8 weeks after administration).

The primary safety endpoint is the assessment of adverse events (AEs) associated with the surgical administration of eladocagene exuparvovec to pediatric subjects using the SmartFlow MR-compatible ventricular cannula at the end of Trial Phase (8 weeks after administration).

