7.2.2. Safety of Surgical Administration Using the SmartFlow Cannula

Adverse events associated with the surgical administration of eladocagene exuparvovec to pediatric subjects using the SmartFlow MR-compatible ventricular cannula that occur during the Trial Phase will be collected as described in [Table 1](#).

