2.1. Study Design

This is an open-label study in subjects with AADC deficiency. At minimum, 3 eligible pediatric subjects will be enrolled and receive eladocagene exuparvovec at 1.8×10^{11} vg via SmartFlow Magnetic Resonance (MR)-compatible ventricular cannula in a single operative session. Subjects will receive standard of care for their AADC deficiency during the study. Subjects will undergo Screening and a Baseline Visit before receiving eladocagene exuparvovec by intraputaminal infusion.

Subjects will return for regular visits during the course of the study. This study will have a Trial Phase, an Extension Phase, and a Long-Term Extension Phase. The length of the study, including the screening period, is 63 months (approximately 5 years).

The objectives of this study’s Trial Phase, Extension Phase, and Long-Term Extension Phase are as follows:

- The primary objectives of the Trial Phase are to assess the PD of eladocagene exuparvovec treatment by evaluation of HVA levels and to assess the safety of the SmartFlow MR-compatible-ventricular cannula for administering eladocagene exuparvovec to pediatric subjects with AADC deficiency. The secondary objectives of the Trial Phase are to further assess the PD of eladocagene exuparvovec in subjects with AADC deficiency using neurotransmitter metabolite assessment and PET analysis. The Trial Phase will be completed 8 weeks after administration of eladocagene exuparvovec.
- The Extension Phase is designed to capture additional clinical information for eladocagene exuparvovec through study evaluations, including changes in motor development, AADC-specific symptoms, and other PD measures. The Extension Phase will be completed at 48 weeks after administration of eladocagene exuparvovec.
- The Long-term Extension Phase is designed to capture long-term safety and efficacy data, for subjects treated with eladocagene exuparvovec, through Month 60.

A data safety monitoring board (DSMB) will conduct a formal review of safety data as outlined in the DSMB Charter. Review by DSMB will not be required to enroll successive subjects. The DSMB will monitor ongoing study results to ensure subject well-being, safety, and study integrity.

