2.3. Study Endpoints

2.3.1. Primary Endpoints

The primary efficacy endpoint is the change from baseline in HVA levels at the end of the Trial Phase (8 weeks after administration).

The primary safety endpoint is the assessment of adverse events (AEs) associated with the surgical administration of eladocagene exuparvovec to pediatric subjects using the SmartFlow MR-compatible ventricular cannula at the end of Trial Phase (8 weeks after administration).

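### The SAP's AESI definition leaves out the protocol's neurosurgical group without declaring it, and no AE summary in the SAP text applies the Week 8 limit of the primary safety endpoint

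*SAP*

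**What the plan says.** **AESIs.** Protocol 7.5.3 has three subsections: risks of the neurosurgical procedure (7.5.3.1), dyskinesia (7.5.3.2) and CSF leaks (7.5.3.3). Under 7.5.3.1, events tied to the neurosurgery and the infusion are to be reported as AESIs. Events arising from general surgical or anesthetic risk are excluded. Protocol 8.3.2.2 includes in the primary safety analysis summaries by "relationship to cannula device, to gene therapy, and to neurosurgical procedure, and AEs of special interest". SAP 7.1.1 lists "TEAE of special interest (TEAESI: dyskinesia and cerebrospinal fluid leakage"). SAP 4.4 declares no change to the protocol-specified analyses.

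**Window.** SAP 2.3.1 states: "The primary safety endpoint is the assessment of adverse events (AEs) associated with the surgical administration of eladocagene exuparvovec to pediatric subjects". It sets the same time limit as Protocol 2.3: "ventricular cannula at the end of Trial Phase (8 weeks after administration"). Protocol 7.2.2 refers to events with the "MR-compatible ventricular cannula that occur during the Trial Phase will be collected as described in" its Table 1, and SAP 2.1 says "The Trial Phase will be completed 8 weeks after administration of eladocagene exuparvovec".

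The analysis text has no such limit. Protocol 8.3.2.2 says: "The primary safety analysis will focus on TEAEs that are defined as AEs with a start date after or worsen after receiving eladocagene exuparvovec". It adds: "Serious Adverse Events will be summarized using SOC and PT". Protocol 8.3 runs summaries from dosing to the end of follow-up. SAP 7.1 takes in AEs to the end of the reporting period, and SAP 7.1.1 treats any post-dose AE as treatment-emergent.

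**The concern.** The study exists largely to answer a safety question about one cannula, over one stated period. Two parts of the planned output do not line up with that question.

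First, the AESI group that the SAP omits is the one closest to the cannula. Protocol 7.5.3.1 names bleeding and infection where the infusion is made as risks of the neurosurgery, the infusion and the cannula. Someone who turns to the AESI tables expecting the protocol's definition would not find these events there, and SAP 4.4 gives no warning of the difference.

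Second, the primary safety endpoint covers 8 weeks, but the tables as written accumulate to Month 60. A table of device-related or procedure-related events over the whole study answers a related question, but not the one the endpoint poses.

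**Working it through.** There is no stated figure to reproduce. The check sets the passages side by side.

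**1. AESI groups.** Protocol 7.5.3 has 3: neurosurgical procedure and infusion, dyskinesia, CSF leak. SAP 7.1.1 has 2: dyskinesia and CSF leak. 3 − 2 = 1 group is missing, and SAP 4.4 does not record it.

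**2. Summaries that Protocol 8.3.2.2 assigns to the primary safety analysis, against the SAP 7.1.1 tables.**

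| Protocol 8.3.2.2 summary | Table in SAP 7.1.1? | Limited to Week 8? |
|---|---|---|
| TEAEs by SOC and PT | yes | no |
| By severity | yes | no |
| Related to the device | yes | no |
| Related to gene therapy | yes | no |
| Related to the neurosurgical procedure | yes | no |
| AESIs | yes, 2 of 3 groups | no |
| SAEs by SOC and PT | yes | no |

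All seven have a table and none has the limit. The other 11 − 7 = 4 tables (PT by descending incidence, F-DOPA-related, leading to withdrawal, gene-therapy-related serious events) have none either. Nor do the 11 items of the overall summary.

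**3. How the SAP treats time elsewhere.** SAP 6.1 ties the primary efficacy analysis to Week 8, and SAP 5.1 reports disposition by phase. The AE section has no counterpart to either and names no primary safety analysis.

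**4. Where the window mismatch starts.** Protocol 2.3 sets Week 8, while Protocol 8.3.2.2 gives a start and no end, and Protocol 8.3 runs to the end of follow-up (Month 60, Week 260). The SAP carries both forward.

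**5. A uniform cut-off day.** SAP 4.3 defines Study Day, on or after dosing, as assessment date minus dosing date plus 1. Eight weeks after dosing is 8 × 7 = 56 days, so Study Day 56 + 1 = 57. Protocol Table 1 gives the Week 8 visit a window of ±3 days, that is Days 54 to 60 if the target is Day 57, and lets a visit spread over 3 days. A cut at the visit would therefore give subjects different windows.

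**6. Order of the counting rules.** For repeated episodes, the SAP 7.1.1 tables count only the most severe or most strongly related one. As a constructed example, one subject has the same PT at Grade 1 in Week 3 and at Grade 3 in Week 60. If the most severe episode is kept first and the cut made afterwards, 0 subjects fall in the window. If the cut comes first, 1 does. With the planned minimum of 3 subjects, that is 0/3 = 0% against 1/3 = 33%.

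**The case against.** The best case for the plan is that nothing of substance is missing.

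- **AESIs.** Protocol 7.5.3.1 defines the neurosurgical group largely by relatedness, and SAP 7.1.1 tabulates procedure-related TEAEs by SOC and PT. Much of the group is therefore reported under another name. This stands, and it limits the harm. A reader might infer that these events go unreported, but the procedure-related tables and the per-subject AE listings rule that out. The overlap is not complete, however. An infusion event may be attributed to the device instead, and the procedure-related table states no exclusion of general surgical and anesthetic events. The difference in definition also remains undeclared.
- **Window.** A reader might infer that the sponsor can choose the cut-off after seeing open-label data. The documents do not support this, because both fix it at Week 8 in the endpoint itself. A reader might also infer that no Week 8 table will exist. That cannot be known: SAP 8 places the table shells in a separate document, which may contain one. The supportable statement is that the SAP text specifies no such cut.
- **Optional summaries.** Protocol 8.3 allows summaries at a timepoint agreed with a health authority, and SAP 4.2 allows data summaries during the study for regulatory purposes. Both are optional, and neither is tied to Week 8.
- **Scale.** The study plans at least 3 subjects, tests no formal hypothesis according to Protocol 8.1, and lists every AE. A Week 8 count can be rebuilt from onset dates. This is fair and keeps the severity low. A rebuilt count still needs the order of rules in step 6, which the SAP does not state.

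**Conclusion.** Both parts hold on the text, at minor to should-fix severity.

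The AESI part is the firmer. One of three protocol-defined groups is absent from a summary that the protocol places in the primary safety analysis, and SAP 4.4 does not say so.

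On the window, the endpoint is clear and the analysis that applies it is not written down. A reader might conclude that the statement in SAP 4.4 is false here too. It is not, because the SAP follows Protocol 8.3.2.2, where the mismatch begins.

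No estimate of how many events would fall outside the window is possible: the documents give no basis for an event rate, and none is claimed. The conclusion rests on the SAP text alone, with the table shells unseen.

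**What to change.** **AESI definition, SAP 7.1.1.** Define treatment-emergent AESIs by the three groups of Protocol 7.5.3, keeping the 7.5.3.1 exclusion of general surgery and anesthesia events. Otherwise, declare and justify the two-group definition in SAP 4.4.

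**Primary safety analysis, SAP 7.1.1.** Name as the primary safety analysis a Trial Phase cut, with onset from the first infusion through Study Day 57 for every subject.

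- Apply it to at least the device-related and procedure-related TEAE tables and the AESI and SAE tables. The remaining Protocol 8.3.2.2 summaries may be cut the same way.
- Apply the window before the one-episode-per-subject rule.
- Keep the whole-study tables as additional summaries; the cannula-safety objective in Protocol 2.1 has no time limit.
- Record the window in SAP 4.4, and align Protocol 8.3.2.2 at the next amendment.

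**Cost.** A short SAP edit, a few extra cuts of tables already planned, and possibly a higher AESI count. No amendment is needed for this alone. Protocol 7.5.4 already has onset date, severity and seriousness recorded. It lists relationship to gene therapy and to surgery but not to the cannula, which Protocol 7.5.5 asks the investigator to assess. The eCRF field behind the device-related table should therefore be confirmed.
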